8.3 Deaths, Serious Adverse Events, and other Significant Adverse Events

All deaths during the study will be listed by treatment group and subject and will include the primary cause of death. Serious AEs and other significant AEs, including those that led to interruption or withdrawal of the study drug, will be provided in separate subject data listings.

8.4 Pregnancies

Listings of pregnancies, if any, and outcomes will be presented.

8.5 Intraocular Pressure

For study eye, pre and post-injection IOP as well as the change from baseline to post baseline values will summarized, using mean, standard deviation, median, and range, by treatment group and protocol specified visit. IOP data will be listed by treatment, subject ID, study eye or non-study eye, and time point.

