4.1.3 Administration of Study Intervention

All participants will be treated starting on Day 1 through Week 92 according to their respective treatment group. The IRT will determine the dosing schedule and adjust it in consideration of missed visits, out of window visits, and missing data during a visit. If a visit is missed at which study treatment is scheduled to be administered, the missed dose should be made up as close to the originally scheduled visit as possible using an unscheduled visit. Adjustments to study intervention due to development of sight-threatening complications of DR are described in Section 4.1.3.1.

As shown in the dosing regimen schematic provided in Figure 1, participants will be treated according to the group to which they were randomized, as follows:

• Group A - KSI-301 5 mg via Intravitreal Injection:

Intravitreal KSI-301 5 mg injection will be administered on Day 1, Week 8, Week 20, Week 44, Week 68, and Week 92.

• Group B - Sham Injection:

To preserve study masking, sham injections are administered to Group B participants at visits in which KSI-301 is administered to Group A participants. Thus, sham injections will be administered on Day 1, Week 8, Week 20, Week 44, Week 68, and Week 92.

For all study participants, non-treatment study visits will occur on Week 32, Week 48, Week 56, Week 80, and Week 96. A final safety assessment will occur on Week 100 and will be done via telephone call for all participants, except in WOCBP, in which case a site visit is required to administer a pregnancy test.

		Year 1								PE				
Week		0	(4)	8	(12)	(16)	20	(24)	(28)	32	(36)	(40)	44	48
KSI-301 5 mg	Q24W													
Sham		0		0			0						0	
						Ĩ	Year 2						SE	SA
Week		(52)	56	(60)	(64)	68	(72)	(76)	80	(84)	(88)	92	96	100 ª
KSI-301 5 mg	Q24W													
Sham						0						0		

Figure 1: Protocol KS301P106: Masked Dosing Regimens by Week

Abbreviations: PE = primary endpoint; Q24W = once every 24 weeks; SA = safety assessment; SE = secondary endpoint.

^a Week 100 is a final safety assessment that will be done via telephone call for all participants, except in WOCBP, in which case a site visit is required for the safety assessment that includes a pregnancy test.

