8.0 SAFETY EVALUATION

Safety analyses will be performed for the Safety Analysis Set. In the Primary Analysis, safety data from Day 1 to Week 48 will be summarized by treatment group.

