8.1 Exposure to Study Medication

Study eye exposure to study medication will be summarized (open-label KSI-301 5mg treatment will not be included here). Summaries will include:

- Mean (SD) and median number of injections, and number of patients receiving ≥1 injection, 1, 2, 3, 4, 5, etc. of KSI-301 or sham injections from Day 1 to Week 48 and from Day 1 to the end of study.
- Duration of study drug exposure (mean [SD] and median, in months) for subjects receiving KSI-301 5 mg or sham.
- Listings will include treatment (KSI-301, sham) and date of injection.

For patients who develop sight-threatening complication(s), exposure to open-label KSI-301 5mg treatment will be summarized and listed similarly as above.

A listing of patients who received study treatment other than the one assigned at randomization will include the randomized treatment, the actual administered treatment, Visit, and study Day. A separate listing will list patients who receive open-label KSI-301 5mg treatment with the same variables.

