8.2 Adverse Events

Adverse events (AEs) will be coded to a MedDRA version 23.1 or later. AEs and Serious AEs (SAEs) will be summarized and listed by ocular events for the treated eye (or study eye), ocular events for the non-treated eye (or fellow eye), and non-ocular (systemic) events.

Treatment emergent AEs (TEAEs) are events with onset date on or after the initiation of study treatment through the last dose date of study treatment + 28 days, start date of non-study anti-

VEGF in study eye on or after last dose date, or start date of open-label KSI-301 treatment due to development of sight-threatening complication, whichever occurs first.

If the severity score of an adverse event is missing, the severity score will be imputed as severe. If the relatedness of an adverse event is missing, the adverse event will be considered related.

At each level of summarization (e.g., any AE, system organ class, and preferred term), subjects experiencing more than one TEAE will be counted only once. In the summary of TEAEs by severity grade, subjects will be counted once at the highest severity reported at each level of summarization.

Frequency tables including patients' incidence rates will be provided through Week 48 for the following:

- Ocular TEAEs and treatment-emergent serious AEs (TESAEs) (study eye and fellow eye separately)
- Non-ocular TEAEs and TESAEs
- Ocular TEAEs leading to study treatment discontinuation (study eye and fellow eye separately)
- Ocular TEAEs by severity (study eye and fellow eye separately)
- Non-ocular TEAEs by severity
- Related ocular TEAEs (study eye and fellow eye separately) by severity
- Related non-ocular TEAEs by severity
- Intraocular inflammation TEAEs and TESAEs not associated with infection, autoimmunity, drug toxicity, or traumatic etiologies (study and fellow eye separately).
- IOI TEAEs and TESAEs associated with infection (study and fellow eye separately).
- IOI TEAEs and TESAEs associated with autoimmune, drug toxicity, or trauma (study and fellow eye separately).
- Arteriothromboembolic (ATE) Adverse Events. ATEs will be tabulated as those events meeting the Anti-Platelet Trialists' Collaboration criteria (i.e., nonfatal

myocardial infarction, nonfatal stroke, and vascular death, including deaths of unknown cause)

- Adverse events of special interest [AESI] (study eye, fellow eye and non-ocular combined), as defined in the protocol Section 8.3.6
- Injection procedure related TEAEs and TESAEs in study eye

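### The IOP summary in SAP 8.5 has no cut at the open-label switch, so sham participants' readings after real KSI-301 injections fall in the sham column

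*SAP*

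**What the plan says.** SAP 8.5 covers study-eye IOP: "pre and post-injection IOP as well as the change from baseline to post baseline values will summarized". The planned statistics are the median, range, mean and SD. The breakdown is "by treatment group and protocol specified visit". The only general time rule is in SAP 8.0: "safety data from Day 1 to Week 48 will be summarized by treatment group". Neither section mentions the open-label switch.

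Other parts of the SAP do separate that period:
- The exposure summary in SAP 8.1 states that "open-label KSI-301 5mg treatment will not be included here", and open-label exposure gets its own summary.
- The TEAE window in SAP 8.2 closes at the earliest of several dates, one being the "start date of open-label KSI-301 treatment due to development of sight-threatening complication, whichever occurs first".
- SAP 7.3 censors the additional secondary efficacy data after an intercurrent event. SAP 7.4 (Table 5) describes CST and BCVA separately before and after the move to the second schedule.

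Under protocol 4.1.3.1, a participant in either arm who develops DME, PDR or ASNV in the study eye starts open-label KSI-301 at the diagnosis visit. SoA-B schedules an ophthalmic exam with IOP and a post-injection IOP at every open-label injection visit. On the masked schedule, protocol 4.1.3 says that "non-treatment study visits will occur on Week 32, Week 48, Week 56, Week 80, and Week 96".

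**The concern.** Protocol Table 2 names increased intraocular pressure as a risk of the injection method. A sham procedure uses no needle and puts nothing into the eye (protocol Table 4), so the sham column shows what IOP readings look like without an injection. Once a sham participant switches, that person's readings follow real KSI-301 injections. Left under sham, they make the two columns look more alike on post-injection IOP than the masked treatments were.

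The range is the most exposed statistic, because one high reading after an open-label injection can set the sham maximum. The open-label safety summary in SAP 8.2 does not fill the gap: it covers study-eye ocular TEAEs and TESAEs and has no IOP table.

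**Working it through.** The plan states no figure for this point, so there is none to reproduce. The check uses the two schedules and a simple mixture formula.

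**Inputs.** Masked injections up to Week 48 are on Day 1 and at Weeks 8, 20 and 44; Weeks 32 and 48 are visits without injection (protocol 4.1.3). Open-label injections are at the diagnosis visit and 4, 16, 28 and 40 weeks later (SoA-B). For diagnosis at a scheduled visit, injection week = diagnosis week + 0, 4, 16, 28 or 40, kept if no later than 48.

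| Diagnosis week | Open-label injection weeks up to 48 | Number | Of these, on a masked-schedule week |
|---|---|---|---|
| 8 | 8, 12, 24, 36, 48 | 5 | 8, 48 |
| 20 | 20, 24, 36, 48 | 4 | 20, 48 |
| 32 | 32, 36, 48 | 3 | 32, 48 |
| 44 | 44, 48 | 2 | 44, 48 |
| 48 | 48 | 1 | 48 |

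**What follows if rows are by week.**
- *Weeks 8, 20 and 44, post-injection.* Both arms have masked readings. The affected sham readings come only from eyes diagnosed that day, because later open-label doses nominally fall at Weeks 12, 24, 36 and 48.
- *Weeks 32 and 48, post-injection.* Neither arm has a scheduled masked injection. Scheduled readings in either column come from open-label KSI-301: at Week 32 from eyes diagnosed that day, at Week 48 from all five paths.
- *Week 48, pre-injection.* Sham eyes still on the masked schedule, or diagnosed that day, are mixed with sham eyes that switched at Weeks 8, 20, 32 or 44.
- *Day 1.* Not affected.

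If SoA-B visits get rows of their own, sham-column readings in rows after the diagnosis visit all follow KSI-301. The SAP does not say which layout applies; the window mapping in SAP 5.8 is written for efficacy analyses.

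**Size at Weeks 8, 20 and 44.** Let q be the share of sham post-injection readings at a visit that come from eyes diagnosed that day, and d the mean difference in post-injection IOP between a real and a sham injection. Then the shift of the sham mean = q × d, and the apparent difference between arms = (1 − q) × d.

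Neither q nor d is in the documents. Purely as an assumption, take q = 5% to 10% and d = 1 to 5 mmHg:
- q = 5%, d = 1: shift 0.05 × 1 = 0.05 mmHg; difference 0.95 instead of 1.
- q = 10%, d = 3: shift 0.10 × 3 = 0.30 mmHg; difference 2.70 instead of 3.
- q = 10%, d = 5: shift 0.10 × 5 = 0.50 mmHg; difference 4.50 instead of 5.

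Here q is a same-visit share. The cumulative share of sham eyes that have switched must not be used in its place. The cumulative share matters for the Week 48 pre-injection row, but there the relevant effect is the pre-injection IOP difference between treated and untreated eyes, for which the documents give neither size nor direction.

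**The case against.** The case for leaving the section alone has several parts.

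- *The table layout is open.* SoA-B visits are named by time since diagnosis, and the Safety Analysis Set groups by treatment actually received, so the readings might not land under sham. This stands as a gap: there is no rule for a participant who begins on sham and later receives KSI-301. Moving that person to the KSI-301 column would put sham-period readings there. A diagnosis visit can also be an ordinary masked-schedule visit. An explicit rule is needed on either reading.
- *The summary is descriptive.* This stands. SAP 8.5 plans no test or estimate of an arm difference, so what is affected is the comparison a reader makes between columns.
- *The risk is captured elsewhere.* This partly stands. IOP rises reported as adverse events fall under the TEAE rules, with a separate post-switch summary, and IOP and open-label injections are both listed, so the split can be rebuilt from listings. The summary table would still mix the periods.
- *Weeks 32 and 48 look worse than they are.* A reader might infer that the comparison there is wholly biased, because scheduled sham-column post-injection readings at those weeks follow real injections. The documents do not support that: neither arm has a scheduled masked post-injection reading then, so there is no masked comparison to bias.
- *ATE and AESI tables.* A reader might infer that these also count post-switch events under sham, because the bullets read "Arteriothromboembolic (ATE) Adverse Events. ATEs will be tabulated as those events meeting the" and "Adverse events of special interest [AESI] (study eye, fellow eye and non-ocular combined" rather than naming TEAEs. That inference is not secure. Both sit in a list that follows the TEAE definition and counting rules, so loose labelling is a plausible explanation. For systemic events, ending follow-up at a switch driven by disease is itself debatable. This remains a wording question.

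**Conclusion.** The point holds for IOP. Followed as written, SAP 8.0 and 8.5 place sham participants' IOP after real KSI-301 injections in the sham column, while the SAP separates that period for exposure, TEAEs and the additional secondary efficacy endpoints. This rests on reading the treatment-group split as the arm the participant started in, which is the natural reading but is not stated for switchers.

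The effect is a blurred descriptive safety table. On the nominal schedule, contamination of the masked post-injection comparison at Weeks 8, 20 and 44 is limited to eyes diagnosed that day; visit windows and unscheduled diagnoses could change this somewhat. The true size cannot be derived, and the mmHg figures above only illustrate the formula. The efficacy analyses are not affected. The change should be made because it is easy and concerns a named risk; the trial's conclusions do not depend on it.

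**What to change.** In SAP 8.5:
1. End the by-arm masked-period IOP summary, in both arms, at the pre-injection reading of the diagnosis visit.
2. Present IOP from the first open-label injection onward in a separate descriptive table by randomized arm, with rows by time since diagnosis.
3. Show the number of eyes in every row, since the masked table at later visits will describe only eyes not yet diagnosed with a complication before that visit.

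In SAP 8.2, as a wording point only, state whether the ATE and AESI tables use the TEAE window. If they do, extend the open-label summary to ATEs and AESIs. It now covers only study-eye ocular events, so post-switch systemic events would otherwise appear in listings alone.

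The IOP change costs one extra descriptive table and fewer readings in the masked table at later visits. It needs no new data. The ATE and AESI extension, if needed, adds rows to an existing summary.

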Intraocular inflammation	Intraocular inflammation has been reported following treatment with intravitreal anti-VEGF medicines, including KSI-301. Additional details are provided in IB Section 5.4.2.3.	Participants will be monitored following the injection and instructed to report any symptoms suggestive of intraocular inflammation without delay to facilitate early diagnosis and treatment (Section 8.1.4). Participants with active ocular infection or inflammation in either eye (e.g., blepharitis, infectious conjunctivitis, keratitis, scleritis, endophthalmitis) are excluded from this study (Section 5.2.1). Participants with active intraocular inflammation will have study treatment interrupted (Section 7.1.1)						
Hypersensitivity	Hypersensitivity reactions may manifest as rash, pruritus, urticaria, severe anaphylactic/ anaphylactoid reactions, or severe intraocular inflammation. Additional details are provided in IB Section 5.4.2.4.	Participants with known hypersensitivity to intravitreal agents such as aflibercept or ranibizumab or any ingredient of KSI-301 are excluded from this study (Section 5.2.2).						

Table 2:Protocol KS301P106: Risk Assessment

Study Procedures	5	
Risks associated with the method of administration	These risks include endophthalmitis, increases in intraocular pressure, retinal detachment, retinal tear, traumatic cataract, and intraocular hemorrhage. Additional details are provided in IB Section 5.4.2.5.	Proper and aseptic injection technique when administering intravitreal injections will be used (Section 8.1.3). Participants will be monitored following the injection and instructed to report any symptoms suggestive of endophthalmitis or retinal detachment without delay to facilitate early diagnosis and treatment (Section 8.1.4). Intraocular pressure and the perfusion of the optic nerve head will also be monitored and managed (Section 8.1.4). Participants with active ocular infection or inflammation in either eye (e.g., blepharitis, infectious conjunctivitis, keratitis, scleritis, endophthalmitis) are excluded from this study (Section 5.2.1).
Exposure to SARS-CoV-2 virus	Section 2.3.2.1	Section 2.3.2.1

 Table 2:
 Protocol KS301P106: Risk Assessment (Cont'd)

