8.1.4 Post Injection Assessments in the Study Eye

Within 5 minutes after the injection, check vision for count fingers or hand motion.

• Tonometry (between 30 and 50 minutes after injection):

If the IOP is >30 mmHg or has increased by ≥ 10 mmHg from pre-injection, the IOP will be measured again at 60–80 minutes post-injection. If there are no safety concerns, the participant will be permitted to leave the clinic. If the IOP value is of concern to the Investigator, the participant will remain in the clinic and will be managed in accordance with the Investigator's clinical judgment. The latest post-injection IOP measured (prior to any intervention for increased IOP, if applicable) will be recorded on the post-treatment IOP eCRF.

The method of post-injection IOP measurement (such as Goldmann tonometry or Tonopen) must be the same as the pre-injection method and remain the same throughout the study for each participant.

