5.3 Study Definitions and Derived Variables

Unless otherwise specified, the duration of Week 48 analysis is defined as Study Day 1 until Week 48, as it is meant to be inclusive both of study treatments leading to the primary efficacy outcome at Week 48 and of safety assessments in that period.

Baseline values are defined as the most recent values prior to the first dose of study treatment.

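### SAP 8.5 plans no same-visit post-injection IOP change after Day 1 and no count of eyes meeting the protocol's re-measurement trigger, so such eyes are tabulated only if reported as adverse events

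*SAP*

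**What the plan says.** Protocol Table 2 lists pressure rise among the risks of the method of administration: "These risks include endophthalmitis, increases in intraocular pressure, retinal detachment". Protocol 8.1.4 schedules tonometry 30 to 50 minutes after injection and sets a trigger with two parts: "If the IOP is >30 mmHg or has increased by" at least 10 "mmHg from pre-injection, the IOP will be measured again at" 60 to 80 minutes. Of the post-injection readings, only the latest one taken before any pressure-lowering intervention goes to the eCRF.

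For the study eye, SAP 8.5 then states: "pre and post-injection IOP as well as the change from baseline to post baseline values will summarized, using mean, standard deviation, median, and range". These summaries are given per arm at each protocol visit. The section adds that "IOP data will be listed by treatment, subject ID, study eye or non-study eye, and time point". The reference for change comes from SAP 5.3: "Baseline values are defined as the most recent values prior to the first dose of study treatment". IOP categories appear only among the baseline characteristics in SAP 6.2.1 (up to 21, 22-29, above 29 mmHg).

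Protocol 10.3.3 gives a reporting term for an adverse event of high IOP after injection. SAP 8.2 tabulates study-eye ocular events, and those related to the injection procedure, as patient frequencies.

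**The concern.** The risk named in Table 2 is an acute rise in some eyes shortly after an injection. The protocol judges it within the visit, against the pressure just before that injection. The SAP's change measure uses a different reference, and its statistics describe the centre and spread of a group, not how many eyes were affected.

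A sham arm is a good comparator for this question. Yet as written, no planned table based on the measurements gives the number or proportion of eyes or injections, by arm, that met the protocol's own cutoffs. The neighbouring SAP 8.6 does carry a protocol safety threshold (the liver criteria of Appendix 7) into a dedicated listing of subjects. IOP has no equivalent.

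**Working it through.** The plan states no IOP figure, so there is none to reproduce. The check has three parts.

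**1. Reference point.** Masked injections through Week 48 fall on Day 1 and Weeks 8, 20 and 44 (protocol 4.1.3), which makes four. On Day 1, baseline is normally that visit's pre-injection reading, so the two measures of change agree. At the other three they can differ:

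change from baseline = (post − same-visit pre) + (same-visit pre − baseline)

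The second term is visit-to-visit variation. Two invented eyes at Week 20 show the effect:
- Baseline 20, pre 12, post 24: same-visit rise 24 − 12 = 12; change from baseline 24 − 20 = +4.
- Baseline 14, pre 20, post 25: same-visit rise 25 − 20 = 5; change from baseline 25 − 14 = +11.

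The first eye meets the 10 mmHg part of the trigger but looks unremarkable on the planned measure. The second is the reverse.

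**2. Statistic.** Inputs: 120 per arm (SAP 9.0). Assumed, because the documents give no values: SD of change 3 mmHg, and a 15 mmHg rise added in k of the 120 eyes at one visit. The mean shift is 15 × k/120. Median shifts and SDs come from 4,000 simulated arms with normal changes. Intervals for k/120 are exact (Clopper-Pearson).

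| k | Mean shift (mmHg) | Median shift (mmHg) | SD of change (mmHg) | What a count would report |
|---|---|---|---|---|
| 4 | 15 × 4/120 = 0.50 | 0.13 | 3.0 to 4.0 | 3.3% (95% CI 0.9-8.3) |
| 6 | 15 × 6/120 = 0.75 | 0.20 | 3.0 to 4.4 | 5.0% (1.9-10.6) |
| 12 | 15 × 12/120 = 1.50 | 0.42 | 3.0 to 5.4 | 10.0% (5.3-16.8) |

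The SD and the top of the range do react. Neither gives the number of eyes.

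Participants and injections need separate counts. If each injection carried an independent probability p (assumed), the share of eyes with at least one event in four injections would be 1 − (1 − p)^4. That is 3.9%, 7.8%, 11.5% and 18.5% for p of 1%, 2%, 3% and 5%.

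**3. What the recorded value can support.** An eye that does not meet the trigger at 30-50 minutes needs no repeat, so its first reading is recorded. An eye that does meet it is re-measured, and the later reading is recorded unless an intervention came first. Provided repeats follow only from the trigger, every recorded value that meets a cutoff belongs to an eye that triggered. Eyes that settled before the repeat drop out. A count from the eCRF is therefore a lower bound.

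**The case against.** The strongest reply is that the plan already captures these eyes. High IOP after injection has its own adverse event term, protocol 8.3.2 sends events found in study data to the adverse event page, and SAP 8.2 tabulates them by patient. Individual pressures are also listed by treatment and time point, so a reader could count from the listing. The mean same-visit rise in each arm follows from two planned means, given paired readings.

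Much of that stands, and it rules out several stronger readings that a reader might infer:
- *Affected eyes are never counted, or the trial cannot state the proportion.* Not supported. Reported events are tabulated and values are listed. What is missing is a planned table covering rises not reported as events.
- *The protocol defines a pressure spike.* Not supported. Section 8.1.4 sets a trigger for a repeat reading, not an event or an endpoint.
- *The planned analysis has low power or misclassifies eyes.* Not supported. SAP 8.5 is descriptive. It plans no test and applies no 10 mmHg rule to change from baseline, so error rates for such rules would describe nothing in the plan.
- *Make-up injections fall out of the table.* The protocol says that "the missed dose should be made up as close to the originally scheduled visit as possible using an unscheduled visit", but the documents do not say how those visits are labelled in the data, and listings are not windowed (SAP 5.8).
- *The early vision check is lost.* The protocol asks: "Within 5 minutes after the injection, check vision for count fingers or hand motion". The documents do not show that the result is held in the database.

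The reply does not supply a count by arm that is independent of each investigator's decision to report, nor the spread of same-visit change. Subtracting two means cannot recover that spread. Per-injection rates for certain adverse events are promised in protocol 9.4.5 but not specified in SAP 8.2.

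**Conclusion.** The point holds as a minor gap in safety reporting. After Day 1, SAP 8.5 does not summarize change on the scale that protocol 8.1.4 uses. It also plans no count at either 8.1.4 cutoff, so eyes that meet the trigger are tabulated only when reported as adverse events, for which there is a term but no numeric threshold.

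The illustrated shifts rest on an assumed SD, an assumed 15 mmHg rise and assumed proportions of eyes, not on trial data. They show only that the mean and median are insensitive when few eyes are affected. The reference-point argument needs no assumption beyond IOP varying between visits. The primary and key secondary analyses and the adverse event tables are unaffected.

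**What to change.** Keep the planned summaries and the listing. Add to SAP 8.5, by arm, for masked injections through Week 48:

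- (a) summary statistics of post-injection minus same-visit pre-injection IOP;
- (b) the number and percentage of participants, and of injections, with recorded post-injection IOP above 30 mmHg or with a rise of at least 10 mmHg from same-visit pre-injection IOP, each cutoff shown separately and make-up injections included.

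Footnote the table to say that the eCRF holds only the latest reading before any intervention, so rises that settle before the 60-80 minute repeat are undercounted.

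Both cutoffs are the protocol's own, and no change to any clinical rule is proposed. The cost is some SAP wording and one more descriptive table from values already collected. The downside is that the counts are a lower bound and must be read as such.
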